**Safety monitoring:**

The study is low risk. However, the research team will monitor the safety of subjects during study procedures. In the event of injury related to this research, treatment will be available through the UIC Medical Center. However, the patient or third party payer, if any, will be responsible for payment of this treatment. Patient subjects will remain under the care of their usual provider, who will be available to give them usual care if needed. Any unanticipated problems related to the study procedure will be immediately reported to the IRB.

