**Title: DOUBLE-BLIND PHASE 2 RCT: EFFECT OF ACUPUNCTURE ON PATIENT VULVODYNIA OUTCOMES**

**RESEARCH PROTOCOL**

Dated 8/15/2017

Specific aims are to:

Aim 1. Compare the penetrating needle group and the skin touch placebo needle group for effects on the: (a) primary outcome: vulvar pain (PAINReportIt® average pain intensity, 0-10), and (b) secondary outcomes: dyspareunia (FSFI dyspareunia) and sexual function (FSFI total). We hypothesize that controlling for baseline values, at posttest there will be statistically significant less vulvar pain (primary) and dyspareunia and better sexual function in the penetrating needle group compared to the skin touch placebo group.

Aim 2. In subjects with a clinically meaningful reduction in pain intensity (at least 1.5 points) at posttest compared to pretest, describe the duration of the acupuncture treatment and placebo effects weekly until pain returns to pretest or up to 12 weeks after posttest. We will describe the variability over time in vulvar pain intensity (0-10) after a tampon insertion-removal stimulus and thereby explore the duration of the effect by intervention group, vulvodynia subgroups, and demographic subgroups (e.g., age, race, occupation). These findings will provide insights to guide future research on initial and maintenance acupuncture for vulvodynia.

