**Title: DOUBLE-BLIND PHASE 2 RCT: EFFECT OF ACUPUNCTURE ON PATIENT VULVODYNIA OUTCOMES**

**RESEARCH PROTOCOL**

Dated 8/15/2017

however, are regular needles used in routine acupuncture. All participants will be informed that they will receive either real or fake acupuncture and they will not be told what kind of needles they are receiving until they complete the duration of effect portion of the study. Participants in the control group will be offered 10 free real acupuncture sessions with regular (not double-blind) acupuncture needles administered by a second acupuncturist after the end of the 17 weeks. The double blind needles are manufactured by [name], the inventor of the double blind acupuncture needle, and will be sent to us sterilized and packaged to maintain sterility.

All participants will receive 10 acupuncture session, two sessions per week over an approximately 5 week period. Each session will last about one hour. The first and last sessions only, where participants will complete the study questionnaires, are expected to last an additional 30 - 60 minutes. Each acupuncture treatment will consist of 13 acupuncture points, of which 12 points specifically treat problems with the genitals. Once the 13 needles are inserted or placed on the skin in the 13 points, they will remain in place for 45 minutes. The RS will remain with the subjects during the treatment session.

At pre-test, before the first acupuncture session, and at post-test, after the 10th acupuncture treatment, participants will be asked to insert and remove a regular Tampax™ tampon with applicator as a standardized pain stimulus, and will complete the three study measures of vulvar pain and sexual function on a computer or tablet:

- 1) PAINReportIt® computerized program to assess pain intensity as well as collect demographics and medications information
- 2) Female Sexual Function Index (FSFI) to assess dyspareunia and sexual function
- 3) Vulvar Pain Functional Questionnaire to describe the physical dimension of impairment in women with vulvodynia
- 4) At post-test, participants will also complete the Double-Blind Needle Questionnaire for the participants to report whether or not they remained blinded to the type of needle used (penetrating or skin touch placebo).

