Weekly for up to 12 weeks after the 10th treatment session, the subjects will be asked to insert and remove a regular Tampax™ tampon with applicator from their vagina and complete the weekly vulvar pain diary to record their vulvar pain, so that we can determine the duration of the treatment effects.

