**Anticipated risks:**

This study has minor risks. There is a small risk of mild bruising, soreness or bleeding after the real acupuncture needle is withdrawn. There is a risk that participants may experience a negative reaction from acupuncture and thereby experience worse symptoms from participation in the study. Participants may feel mild discomfort upon needle insertion, but this dissipates once the needle has been inserted. To avoid or minimize these risks only experienced licensed acupuncturists will perform the acupuncture. There is a risk that some of the questions in the questionnaires may make the participants uncomfortable, nervous or tired, but they don't need to answer any question they don't wish to answer. There is also the risk of loss of privacy or confidentiality, but we will avoid this risk as much as possible.

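### No systematic recording or by-arm table of adverse events is specified, so the needle harms the protocol itself names have no planned data source

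*Combined protocol and SAP*

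**What the plan says.** The Safety monitoring section gives two operating rules. The first is that "the research team will monitor the safety of subjects during study procedures". The second is that "Any unanticipated problems related to the study procedure will be immediately reported to the IRB". Neither comes with a form, a question, time points, a severity grade or a definition of an adverse event.

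The Anticipated risks section names local harms: "There is a small risk of mild bruising, soreness or bleeding after the real acupuncture needle is withdrawn". It adds discomfort on insertion, and a more general one: "There is a risk that participants may experience a negative reaction from acupuncture and thereby experience worse symptoms from participation in the study".

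The Procedures section lists PAINReportIt, the FSFI and the Vulvar Pain Functional Questionnaire at pretest and posttest, plus the Double-Blind Needle Questionnaire at posttest. It also says "The RS will remain with the subjects during the treatment session", but gives that person no recording task. After session 10, women "complete the weekly vulvar pain diary to record their vulvar pain, so that we can determine the duration of the treatment effects". The Data analysis section covers missing data and an exploratory affective pain score; it has no safety population, harm endpoint or harm table.

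**The concern.** The harms most directly tied to needle penetration are the ones the plan does not arrange to record. Because they are anticipated, the rule for unanticipated problems passes them by. The monitoring rule might notice them, but nothing says how, when or on what record.

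At stake is information that cannot be recovered later. The Background and Purpose section presents this as the first double-blind randomized trial of acupuncture for vulvodynia, and the placebo needle is described under Procedures as not penetrating the skin. A masked placebo arm of this kind is what would allow needle harms to be separated from background complaints. Harms noted only when a woman volunteers them would be incomplete, and could be biased if the person noting them can guess the arm. The Specific aims and Anticipated benefits sections say that the findings will guide future research on initial and maintenance acupuncture, and such research would need harm rates.

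**Working it through.** The plan states no figure on this point, so there is nothing to reproduce. The check is one of text, followed by a scale calculation.

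**1. Named risk against data source**

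| Named risk (Anticipated risks) | Reached by the IRB rule? | Instrument described as recording it | Planned comparison by arm |
|---|---|---|---|
| Bruising, soreness, bleeding | No, anticipated | None | None |
| Discomfort on insertion | No, anticipated | None | None |
| Negative reaction with worse symptoms | No, anticipated | In part: pain, sexual function and functional scores, before and after treatment | In part: Aim 1 compares pain, dyspareunia and sexual function at posttest |

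**2. Why the efficacy scales fill only part of the gap**

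- The main measures are taken at two time points, baseline and straight after session 10 (Study design). A woman who worsens and leaves before session 10 has no posttest score. The likelihood-based handling of missing data uses what was observed; it cannot show that she was harmed.
- No rule requires the reason for leaving to be recorded.
- Losses are expected: up to 130 recruited for full data on 80, after screening and attrition. The split between those two causes is not given.
- The pain diary is described as recording pain. Who completes it is also unclear: Aim 2 describes duration "In subjects with a clinically meaningful reduction in pain intensity (at least 1.5 points) at posttest compared to pretest", while Procedures refers to the subjects without that limit. On the narrower reading, women who worsened would have no diary.

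**3. Scale**

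The number treated per arm is not given. I take 40 (80 split 1:1) and 65 (130 split 1:1) as working values.

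- Exposure in the penetrating arm, if every session is attended: 40 × 10 = 400 sessions and 400 × 13 = 5,200 needle placements; or 65 × 10 = 650 sessions and 650 × 13 = 8,450 placements.
- Upper bound on the per-woman rate with zero events, one-sided 95%: solve (1 − p)^n = 0.05, so p = 1 − 0.05^(1/n). For n = 40, p = 0.072. For n = 65, p = 0.045.
- Power to detect a difference between arms, two-sided 5% level, normal approximation with pooled variance under the null. The event rates are assumptions, since the documents give none:

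| Assumed rates, needle v placebo | 40 per arm | 65 per arm |
|---|---|---|
| 10% v 2% | 32% | 48% |
| 20% v 5% | 53% | 74% |
| 30% v 5% | 85% | 97% |

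At 20% v 5%, the approximate 95% interval for the difference has half-width 1.96 × √[(0.20 × 0.80 + 0.05 × 0.95)/n], which is 0.141 for n = 40 and 0.111 for n = 65. A harm table would be informative, but only large differences would be detected reliably.

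**The case against.** The best case for the plan is that silence is not a decision against recording. The monitoring sentence does not exclude notes of bruising or bleeding, and the research specialist is present at treatment sessions. With two sessions a week, nine of the ten are followed by a return visit at which a problem could be noticed. The trial is phase 2, calls itself low risk, has no safety aim and claims no harm comparison. Asking repeatedly about bruising could also suggest to a woman that she has the real needle, before a self-reported primary outcome.

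Much of this stands, and it limits the point. A reader might infer that the trial can give no harm comparison at all. The documents do not support that, because worsening of symptoms is a named risk and pain and sexual function are compared between arms. A reader might also infer that harms are watched for only during treatment and will be counted in neither arm. The text does not say only, and the weekly tampon procedure extends study procedures up to 12 weeks after posttest. Nor do the documents say that bruising or soreness mostly appears after the woman has gone home; the point does not need it. Finally, the stated use is to guide future research, not to set treatment directly.

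What the objection does not supply is a question, a record or a table. Observation without a recording rule yields no rate. The cueing risk is real, and it shapes the fix rather than removing the need for one.

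**Conclusion.** The point holds in a limited form. The available text specifies no systematic recording of adverse events and no tabulation by arm. Bruising, soreness and bleeding have no planned data source. The only planned comparison touching harm is worsening on the efficacy scales, which misses women who leave before posttest. This does not threaten the primary comparison; it is a gap in collection that is cheap to close now and cannot be closed afterwards.

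In size, zero events of a given kind would allow an upper bound of 7.2% (40 per arm) or 4.5% (65 per arm) on the per-woman rate. Without systematic recording, no such bound can be stated. Both arm sizes are assumptions; the right denominator is all treated women, not the 80 with full data. Any comparison between arms should be read as descriptive.

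One caveat: a part of the document directly after the Anticipated risks section was not available for review, so a rule placed there cannot be ruled out.

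**What to change.** Amend the Procedures, Data analysis and Safety monitoring sections as follows.

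1. At the start of sessions 2 to 10, the research specialist asks every woman in both arms the same open-ended question about any new problem since the last session, and records type, severity and date.
2. State that the research specialist is masked to arm. The protocol says this of the acupuncturist and the subject, but nowhere of the research specialist.
3. Ask the specific items (bruising, soreness, bleeding) once, at posttest, after the primary outcome and the Double-Blind Needle Questionnaire are complete.
4. Cover session 10 with one line in the first weekly diary, or a contact, for every treated woman and not only those who improved by at least 1.5 points. Posttest follows session 10 immediately, so it cannot cover what comes later.
5. Record the reason for every discontinuation.
6. Tabulate women affected by arm, descriptively, among all treated women.
7. Keep the IRB rule as it stands.

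The cost is one short form, one table and, where a woman would otherwise have no diary, one contact. No extra visit is needed. There is a small risk of cueing needle type, which the open-ended wording and the late placing of the specific items limit. Some risk remains for the diary ratings, which come after those items while women are still masked.
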